Department of Otolaryngology and
Communication Sciences
Medical College of Wisconsin
[name]
[name]
[contact]
Email: [contact]

Sub-investigator:

[name]
Associate Professor
Department of Otolaryngology and
Communication Sciences
Medical College of Wisconsin
[name]
[name]
[contact]
Email: [contact]

Sub-investigator:

[name]
Professor
Department of Radiation Oncology
Medical College of Wisconsin
[name]
[name]
[contact]
Email: [contact]

Biostatistician:

[name]
Associate Professor
Institute for Health and Society
Division of Biostatistics
[name]
[name]
[contact]
Email: [contact]

Sub-investigator:

[name]
Associate Professor
Electrical Engineering
College of Engineering and Applied
Science
University of Wisconsin-Milwaukee
[name]
[name]
[contact]
Email: [contact]

Funder:

NRG NCORP Grant

PROTOCOL SUMMARY

[figure not shown]
Title	Transdermal Buprenorphine for the Treatment of Radiation-Induced Mucositis Pain in Head and Neck Cancer Patients: A Pilot Study
Principal Investigator	[name] (Study PI)
Clinical Trial Phase	Phase II
Study Population	Stage I-IV by AJCC staging system 8 th edition head and neck squamous cell carcinoma (HNSCC) patients, candidate for curative intent or adjuvant radiation therapy
Primary Objectives	To investigate the efficacy of using FDA-approved doses of transdermal (TD) buprenorphine in combination with oral tramadol to provide adequate pain control in radiation induced mucositis.
Secondary Objectives	
 1. Assess compliance of the study drug regimen. 2. Assess use of off-protocol pain medications during treatment and follow-up period. 3. Compare average weekly pain scores calculated by the oral mucositis (OM) pain app with the average pain scores recorded by the BPI short form. 4. Correlate average weekly pain scores with physical activity as documented on symptoms and functional assessment tools like MDASI-HN. 5. Assess use of nonopioid supportive care medications (i.e., laxatives, antiemetics and oral anesthetics) in conjunction with the study drug combination during treatment and follow-up period. 6. Assess gastrointestinal and cognitive side effect profile of study drug combination and its impact on cognition and quality of life. 7. Evaluate safety of the study drug combination.
Primary Endpoint	Establish efficacy of study regimen by showing that at least 33% of patients will achieve at least 30 percent decrease in visual analog scale (VAS) pain score of BPI questionnaire from baseline to the end of week 9 of treatment and follow-up period.
Secondary Endpoint	
 1. Monitor compliance of study drug regimen through the OM Pain App and medication diary. 2. Identify study participants that require off protocol opioids for pain control despite being on highest dose of study drug combination. 3. Correlate cumulative mean weekly pain scores calculated by the pain app with the average weekly pain scores recorded by the BPI short form. 4. Correlate average weekly OM Pain App scores and average weekly pain scores calculated from BPI short form and the MD

	
Anderson Symptom Inventory - Head & Neck (MDASI-HN), which is a head and neck symptom and function evaluation tool.
 
 5. Maintain a weekly log of use of other nonopioid medication, such as laxatives, antiemetics, and oral anesthetics in conjunction with the study drug combination during treatment and follow-up period through weekly questionnaires. 6. Assess incidence and severity of gastrointestinal and cognitive adverse events measured by weekly PROMIS® (GI and cognition) questionnaires to better characterize the side effect profile of the drug regimen and its impact on quality of life. 7. Safety: Assess incidence and severity of adverse events associated with study drug combination, using the CTCAE version 5. 								
Main Criteria	
Inclusion
 
 1. Age >18 years. 2. Histologically confirmed malignancies of Head and Neck involving Stage I-IV by AJCC staging system 8th edition (oral cavity, oropharynx, nasal or paranasal sinuses, hypopharynx and larynx etc.) including both squamous and non squamous cell histology's (salivary gland carcinomas and carcinomas of unknown primary will be included) 3. Undergoing a course of either definitive radiation (dose of at least 50 Gy to the head and neck region) with or without chemotherapy or adjuvant radiation (at least 50 Gy to the head and neck region) with or without chemotherapy (patients with a history of prior definitive course of radiation will be allowed). 4. ECOG Performance status ≤ 2. 5. Concurrent enrollment on an interventional trial is allowed. 6. English speaking and literate. 7. Patients will be allowed to take radiotherapy mix, viscous lidocaine or magic mouthwash-like agents that do not contain opioids. Tylenol® allowed for fever. 8. Adequate organ function: Minor dose adjustments for tramadol are required in cases of severe liver and renal impairment so we would only include patients with adequate organ function outlined in table below. No dose adjustment for renal or hepatic impairment is required for TD buprenorphine. Some other parameters like hemoglobin, platelets, and WBC are required for administration of standard-of-care chemotherapy, such as cisplatin along with radiation in treatment of HNSCC. They are not required for administration of buprenorphine or tramadol. 
 
Organ Function Table
 
 
 Adequate hepatic function:	
 
 total bilirubin	< 2 mg/dL	
 
 AST(SGOT)/ALT	< 5 times institutional upper limit	
 
 Adequate renal function:	
 
 
	Adequate hepatic function:		total bilirubin	< 2 mg/dL	AST(SGOT)/ALT	< 5 times institutional upper limit	Adequate renal function:	
Adequate hepatic function:									
total bilirubin	< 2 mg/dL								
AST(SGOT)/ALT	< 5 times institutional upper limit								
Adequate renal function:									

	creatinine clearance	> 30 mL/min/1.73 m ² for patients with creatinine levels above institutional normal
Main Exclusion Criteria	
 1. Physical exam demonstrating pre-existing mucositis from prior radiotherapy treatments or other causes. 2. Pre-existing oral infection or ongoing toxicity from prior radiotherapy. History of opioid abuse disorder, confirmed by medical history or subject disclosure. positive urine drug screen at screening visit. Exceptions will be made for subjects with current prescriptions post-surgery or other medical intervention. Previous history of allergic reaction to buprenorphine and tramadol. 3. Patients with multiple distant metastasis. (Patients with resectable oligometastasis will be allowed). 4. Current or recent use of short or long acting mixed opioid agonists/antagonists or other opioid antagonists. (Treatment with more than 2 doses of short acting oral or intravenous opioids like Oxycodone, morphine or hydromorphone within 24 hours of screening). Patients on treatment with long-acting opioids like fentanyl patch, methadone, oxycodone extended release, morphine extended release within 72 hours of screening would be excluded. Patients presenting with any other cause of pain not related to radiation-induced mucositis or head and neck cancer VAS >4/10 on BPI questionnaire (question 3: worst pain in last 24 hours) on the day of enrollment requiring opioid medications for pain control. 5. Prolonged QTc greater than 450 milliseconds in males and greater than 470 milliseconds in females at the time of enrollment. 6. Patients receiving induction chemotherapy prior to or after radiation/chemoradiation; such as patients with nasopharyngeal carcinoma. 7. Patients with a history of abdominal surgery within 60 days of registration or acute gastrointestinal conditions, such as colitis and appendicitis within four weeks of registration. 8. Conditions that may compromise the blood-brain barrier permeability. The blood-brain barrier may become leaky in select neurological diseases, such as amyotrophic lateral sclerosis, epilepsy, brain trauma, and brain edema. 9. Patients with a history of myocardial infarction ≤ 6 months prior to registration. 10. Patients with a history of significant respiratory depression; acute or severe bronchial asthma; known or suspected gastrointestinal obstruction, including paralytic ileus. 	

Study Design	Single-arm prospective clinical trial to determine the efficacy of transdermal buprenorphine and oral tramadol drug combination in alleviating radiation-induced mucositis pain in head and neck cancer patients during treatment and the follow-up period.
Study Agent	Transdermal buprenorphine with oral tramadol.
Number of Subjects	20
Estimated Time to Complete Enrollment:	Approximately 12 months.

STUDY SCHEMA

STUDY CALENDAR

Procedure	Screening ¹	Weeks During Chemoradiation (± 3 days)						Weeks follow-up period ² (± 3 days)					
		1*	2	3	4	5	6	7	8	9	10	11	12
Study Day/Visit Day													
Informed consent	X												
Baseline medical conditions	X												
WHO grade mucositis [#]	X	X	X	X	X	X	X	X	X	X			X
Oral exam for presence of other causes of mucositis (oral candidiasis, infections, trauma), etc.	X	X	X	X	X	X	X	X	X	X			X
Urine drug screen	X												
CBC with differential	X	X	X	X	X	X	X	X	X	X			X
CMP ³	X	X	X	X	X	X	X	X	X	X			X
Opioid use and nonopioid drug use log ⁴		X	X	X	X	X	X	X	X	X	X	X	X
OM Pain App assessment ⁵	X	X	X	X	X	X	X	X	X	X	X	X	X
Pain app compliance questionnaire		X	X	X	X	X	X	X	X	X	X	X	X
Monitor WI PDMP website for opioid use	X	X	X	X	X	X	X	X	X	X	X	X	X
Medical history/stage of disease	X												
Weight	X	X	X	X	X	X	X	X	X	X	X	X	X
Performance status/ECOG	X												X
PROMIS® GI and cognition scoring ⁶		X	X	X	X	X	X	X	X	X	X	X	X
BPI(Brief Pain Inventory) score	X	X	X	X	X	X	X	X	X	X	X	X	X
MDASI-HN ⁶		X	X	X	X	X	X	X	X	X	X	X	X
Review device usage and proper reporting ⁶		X	X	X	X	X	X	X	X	X	X	X	X

Procedure	Screening ¹	Weeks During Chemoradiation (\pm 3 days)						Weeks follow-up period ² (\pm 3 days)					
		1*	2	3	4	5	6	7	8	9	10	11	12
Study Day/Visit Day													
EKG ⁷	X						X						X
Digital image collection of oral cavity to evaluate mucositis ⁸	X				X				X				X
Record type of caloric intake (normal, soft, liquid, parental/enteral)	X	X	X	X	X	X	X	X	X				X
Report use of IV fluids for hydration	X	X	X	X	X	X	X	X	X				X
Adverse event recording (CTCAE v5)	X	X	X	X	X	X	X	X	X				X
Pregnancy test (HCG) for WOCB	X												

*week 1 starts with the first week of radiation therapy and is continuous without adjustment.
WHO mucositis score will be recorded by the investigators during weekly clinic visits

1. Patients found to be eligible for the study can be screened and enrolled anytime during first six weeks of radiation therapy. VAS pain scores will be recorded weekly using BPI questionnaires and daily using the pain app from the day of enrollment, as outlined in study calendar. Treatment with study regimen, collection of PROMIS[®], MDASI, CTCAE and other assessments like opioid drug use log, as outlined in the study calendar will start once the patient develops mucositis and has VAS \geq 4/10 pain score on the OM Pain App and BPI questionnaire (question 3: your pain at its worst in last 24 hours). Patients usually develop mucositis by the third or fourth week of radiation therapy so we anticipate treatment would begin by fourth week in most patients, but it may start sooner if the patient develops mucositis and has VAS \geq 4/10 pain. If a patient presents with radiation-induced mucositis pain on the day of enrollment, then, all study procedures, including PROMIS[®], MDASI-HN, and CTCAE will be completed that day. Visit procedures that were performed as standard of care prior to consent (without the specific intent to make the subject eligible for the trial), may count toward screening tests and eligibility if they are within the screening window of two days. Clinician follow-up will be scheduled weekly (1–7) and then on weeks 9 and 12.
2. If a subject is off the study drug regimen or the subject withdraws, then they will be followed as per follow-up requirements.
3. Serum chemistry values will include ALT/SGPT, AST/SGOT, alkaline phosphatase, bilirubin (total, direct, and indirect) creatinine, LDH, sodium, potassium, chloride, bicarbonate, calcium, phosphate, magnesium, BUN/urea, albumin, glucose. Serum chemistry results obtained from unscheduled visits should be entered into the electronic database. Additional serum

chemistry testing should be done as clinically indicated.

4. Record of opioid pain medications, laxatives, and antiemetic use from the patient's drug diary will be copied by investigators on weekly clinic visits. This will commence after starting treatment. a) Patients will document pain and supportive medication use data daily in their diaries but that information will be verified and recorded by investigator/research coordinator during weekly clinic visits in the electronic medical record(EMR). This data is currently being collected in a section of pain app. Patients average weekly VAS pain scores (question 3 of BPI questionnaire) will also be documented in EMR during weekly clinic visits as per standard of care and can be used for study purposes.
5. The Oral Mucositis (OM) Pain App will be evaluated by the study team on a daily basis through a real-time pain assessment tool in the mobile app. Patients can start using the OM Pain App before starting therapy to familiarize themselves with the instrument. b) Pain app readings will be recorded up to four times/day. The daily pain data will be analyzed by the UWM research team on a weekly basis.
6. All questionnaires/forms can be recorded on weekly in-person visits from weeks 1–7 then completed weekly through in-person/telephone interviews by CTO staff from week 8–12. Other assessments can also be done over phone during week 8, 10 and 11. Window period of +/-3 days will be allowed for data collection.
7. EKG will be done at screening and then on week 7 and 12 if the patient is on treatment with Buprenorphine patch.
8. Digital photos will be taken to document mucositis on the day of enrollment, treatment initiation, then during week 9 and week 12 clinic visits.

=

LIST OF ABBREVIATIONS

AE	adverse event
ALP	alkaline phosphatase
ALT	alanine aminotransferase
ANC	absolute neutrophil count
AST	aspartate aminotransferase
AUC	area under the curve
BPI	Brief Pain Inventory
BUN	blood urea nitrogen
CBC	complete blood cell (count)
CDK	cyclin-dependent kinases
CQ	chloroquine
CR	complete response
CRC	clinical research coordinator
CRF	case report form
CSF	cerebral spinal fluid
CT	computerized tomography
CTCAE	Common Terminology Criteria for Adverse Events
CTL	cytotoxic T cell
CTO	Clinical Trials Office
DFS	disease-free survival
DLT	dose-limiting toxicity
DSMC	Data and Safety Monitoring Committee
DSMP	data and safety monitoring plan
ER	estrogen receptor
FDA	Food and Drug Administration
GCP	good clinical practice
GVHD	graft-versus-host disease

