4.8 Study Procedures: After starting study drug regimen(Weeks 1–7)

These procedures must be completed weekly during the study. These will be recorded once the patient starts the drug regimen when radiation-induced mucositis pain VAS is greater than 4/10 on the BPI and pain app. The following procedures, such as MDASI and PROMIS® questionnaire administration, and adverse event evaluation, using CTCAE, will also be completed if the patient presents with radiation-induced mucositis pain (VAS \geq 4/10) on the day of enrollment.

- Record WHO mucositis grade.
- Brief Pain Inventory.
- ECOG/Zubrod Performance status.

- MD Anderson Symptom Inventory.
- PROMIS® cognition and GI questionnaires.
- Oral cavity digital image collection to evaluate mucositis will be done on the day of treatment initiation, the end of week 9, and then week 12.
- Record mucositis due to other causes (oral candidiasis, infections, trauma, etc.).
- Record adverse events, using CTCAE v.5.0.
- Record type of calorie intake (normal, liquid, soft, parental/enteral).
- Report use of IV fluids for hydration.
- OM Pain App data monitoring (VAS included in pain app).
- Review OM Pain App device usage and proper reporting.
- Review opioid log and record use of oral anesthetics, laxatives, and antiemetics at home. This data is currently being collected in a section of pain app. Patients average weekly VAS pain scores (question 3 of BPI questionnaire) because of radiation induced mucositis will also be documented in EMR during weekly clinic visits as per standard of care.

- Monitor opioid usage through WIPDMP,
- Review bloodwork, including CBC and CMP.
- EKG will be performed at screening, week 7 and 12 for patients on buprenorphine patch

If a subject stops radiation therapy prior to week 7, visits will remain on the same schedule, Subjects will need to come in for a weekly visit(s).

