11. Patients presenting with any other cause of pain not related to radiation-induced mucositis or head and neck cancer, VAS >4/10 on BPI questionnaire (question 3: worst pain in last 24 hours) on the day of enrollment requiring opioid medications for pain control
12. Patients with a history of myocardial infarction ≤ 6 months prior to registration.
13. Patients with a history of significant respiratory depression; acute or severe bronchial asthma; known or suspected gastrointestinal obstruction, including paralytic ileus.
14. History of serious or severe hypersensitivity reaction to buprenorphine, tramadol or any of its excipients.
15. Use of the following drugs will not be permitted after initiation of study drug regimen: capsaicin, NSAIDS, tetrahydrocannabinol, and cannabinoids. Refer to Section 7 for details on contraindication of drug regimen. Patients will be allowed to participate in the study if they have been using antidepressants like SSRI'S, other antipsychotics and antiseizure medications for at least 4 weeks prior to enrollment on the study. Chronic use of these agents will not affect our primary endpoint of assessing impact of study regimen of Buprenorphine and Tramadol on alleviating acute radiation induced mucositis pain. As per package insert of buprenorphine and tramadol concomitant use of the above-mentioned agents with study pain regimen is not contraindicated. However, clinicians are advised to exercise caution as there have been some rare incidences of serotonin release syndrome (SRS) with concurrent administration of SSRI's and Tramadol. Buprenorphine is also not contraindicated but should be used with caution in patients with h/o seizure disorders. Study regimen can be stopped if SRS or any other adverse event occurs as a consequence of this combination. Periodic EKG's will also be performed to monitor for QTc prolongation.
16. Pregnant and lactating women are excluded from this study because chemotherapy and radiation given for the treatment of HNSCC have a potential for teratogenic or abortifacient effects. Additionally, buprenorphine is classified as category C for use during pregnancy, which means that the risk of adverse effects on the fetus cannot be ruled out. Buprenorphine does cross the placenta, and the use of opioids during pregnancy may result in neonatal withdrawals soon after birth. Symptoms of this may include irritability, apnea, increased tone, tremor, convulsions, or respiratory depression

Subject Initials: _____

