5.4 Drug Regimen Titration Schedule

Table 2 Drug Titration Schedule

Drug: Buprenorphine with tramadol for breakthrough pain (**First seven weeks of study**) $T = 0 - 7$ weeks;

Start TD buprenorphine 5 μ g/hour along with oral tramadol 50 mg to 150 mg (total dose over 24 hours) as needed for breakthrough pain when mucositis related pain is $\geq 4/10$ on VAS measured on OM Pain App and BPI. Further dose adjustments will be made through pain app.

- If VAS is $>3/10$ for 72 hours on tramadol 150 mg (total dose over 24 hours) and buprenorphine 5 μ g/hour, then, increase tramadol to 250 mg (total dose over 24 hours).
- If VAS is $>3/10$ for 72 hours, even with tramadol 250 mg (total dose over 24 hours) and buprenorphine 5 μ g/hour, then, increase dose of buprenorphine to 10 μ g/hour.
- If the pain persists VAS $>3/10$ for 72 hours on tramadol 250 mg (total dose over 24 hours) and 10 μ g/hour, then, increase the dose of tramadol to 350 mg (total dose over 24 hours).
- If VAS pain is $>3/10 \times 72$ hours with both tramadol 350 mg (total dose over 24 hours) and buprenorphine 10 μ g/hour, then, increase dose of buprenorphine to 15 μ g/hour.
- If VAS pain $>3/10 \times 72$ hours on tramadol 350 mg (total dose over 24 hours) and 15 μ g/hour of buprenorphine, then, increase the dose of tramadol to 400 mg (total dose over 24 hours) and buprenorphine to 20 μ g/hour.
- If the pain persists and is unbearable at $>3/10$ for 96 hours, despite being on highest dose of both drugs, then, replace tramadol with oxycodone at the clinician's discretion up to 90 mg (total dose over 24-hour period) for pain relief.
- If VAS is $\leq 3/10$ maintained for 72 hours, then, we can start tapering off total daily tramadol dose by 50 mg every day, but not change the buprenorphine dose during the first seven weeks of treatment, as mucosal injury from ongoing radiation may increase pain later.

(Post-radiation period) $T = 8 - 12$ weeks: if necessary, increase dose of buprenorphine up to 20 mcg along with tramadol up to 400 mg/day as per titration schedule used in the first seven weeks until VAS is $\leq 3/10$. If pain is well controlled (VAS $\leq 3/10 \times 72$ hours), start weekly tapering of buprenorphine by 5 mcg and tramadol by 50 mg daily.

Special Circumstances

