7.1.5 Side Effects

Common side effects (>5%) of buprenorphine include nausea, vomiting, constipation, drowsiness, dizziness, headache, and sweating. It may also cause central nervous system depression, respiratory depression, and QT prolongation. Anticholinergic side effects like dry mouth, miosis, orthostatic hypotension, and urinary retention are also seen. Transdermal patches are also associated with contact dermatitis in some individuals. (42) If QTc prolongation of more than 500 ms is noticed, then, buprenorphine should be held until it is less than 470 ms. If respiratory depression is observed, then, remove buprenorphine patch, give oxygen, administer IV naloxone 2 mg stat over 90 secs in the hospital or urgent care setting.

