7.2.8 Dose Adjustment in Liver Failure

No dose adjustment is required in mild to moderate liver failure (Child Pugh class A and B).

Restrict dose to 50 mg q12 in severe liver impairment. **Refer to Table 4**

Table 4. Dose Modifications of Buprenorphine and Tramadol

Table 4:	Buprenorphine Patch	Oral Tramadol
Organ Impairment		
Renal: Creatinine clearance >30ml/min.	No dose adjustment.	No dose adjustment.
Renal: Creatinine clearance <30ml/min.	No dose adjustment.	Restrict maximum daily dose of tramadol immediate release to 200 mg/day.
Mild to moderate liver failure (Child Pugh class A and B).	No dose adjustment.	No dose adjustment.
Severe liver failure (Child Pugh C).	Not studied in severe impairment.	Restrict dose to 50 mg q12 in severe liver impairment.
Cytopenia's (any grade).	No dose adjustment required.	No dose adjustment required.
Other side effects, such as severe nausea, vomiting, headache, respiratory depression, somnolence, dizziness, and constipation.	Dose adjustment at clinician's discretion.	Dose adjustment at clinician's discretion.
Prolonged QTc>500 msec attributable to buprenorphine (other causes ruled out).	Hold buprenorphine patch until QTc comes back to normal range <470 msec	Not applicable

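### EKGs fall at radiation weeks 7 and 12 and only on the patch, so some patients can pass through 20 mcg/h unmeasured and, read literally, a QTc hold has no scheduled EKG to end it

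*Combined protocol and SAP*

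**What the plan says.** - **EKG schedule.** Footnote 7 of the Study Calendar: "EKG will be done at screening and then on week 7 and 12 if the patient is on treatment with Buprenorphine patch". Sections 4.8 and 4.9 repeat it: "EKG will be performed at screening, week 7 and 12 for patients on buprenorphine patch".
- **Clock.** The calendar note reads "week 1 starts with the first week of radiation therapy and is continuous without adjustment". Visits have a window of 3 days either way.
- **Drug start.** Section 4.10 lets the regimen start at any point in the first six weeks of radiation; Section 5.1 says at any point during radiation. Most patients are expected to start by week 4.
- **Titration.** Table 2 (Section 5.4) moves in 72-hour steps and continues in weeks 8 to 12. For controlled pain in that later period it says "start weekly tapering of buprenorphine by 5 mcg and tramadol by 50 mg daily".
- **QTc rules.** Section 7.1.5: "If QTc prolongation of more than 500 ms is noticed, then, buprenorphine should be held until it is less than 470 ms". Table 4: "Hold buprenorphine patch until QTc comes back to normal range <470 msec". Section 6.1.1 lists QTc above 500 ms among the study's adverse events. Exclusion 15 in Section 4.10, on patients taking antidepressants or antipsychotics, says "Periodic EKG's will also be performed to monitor for QTc prolongation" and gives no timing.
- **Analysis.** Section 8.3 uses all treated patients for safety. Section 8.6 tabulates adverse events as counts with percentages.

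**The concern.** The EKG dates follow radiation, whereas the QTc rules concern the patch. No EKG is tied to the first patch, to a dose increase or to the top dose, so whether a patient is measured at the highest dose depends on when mucositis pain began and how fast the dose rose. The on-patch condition creates a second gap: the end of a hold needs a QTc value, but a patient on hold is not wearing the patch.

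Two things are at stake. The EKGs that exclusion 15 offers as a safeguard may miss the period they are meant to watch, in a trial with no formal stopping rule (Section 8.7). And the QTc line of the safety table would treat a patient who never had an on-drug EKG the same as one measured and found normal. The primary pain endpoint is not affected.

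**Working it through.** The plan states no EKG coverage figure, so there is none to reproduce. The check is calendar arithmetic.

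**Inputs.** Day 1 is the first day of radiation, and week w is days 7w − 6 to 7w. Week 7 is days 43–49 (40–52 with the window). Week 12 is days 78–84 (75–87 with the window). Table 2 has five 72-hour steps up to 20 mcg/h. Tramadol is replaced by oxycodone after a further 96 hours, and the patch can come off after another 72 hours. Buprenorphine is not tapered in the first seven weeks, so the first cut is on day 50 at the earliest.

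**Formulas, for start day s at the fastest pace.**
- 20 mcg/h reached: s + 5 × 3 = s + 15
- Failure route, patch off: s + 15 + 4 + 3 = s + 22
- Taper route, leaves 20 mcg/h: the later of s + 15 + 3 = s + 18 and day 50
- Taper route, patch off: three weeks after the first cut (15, 10, 5, 0)

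| Start day | Reaches 20 | Off (failure) | Leaves 20 (taper) | Off (taper) |
|---|---|---|---|---|
| 15 (week 3) | 30 | 37 | 50 | 71 |
| 22 (week 4) | 37 | 44 | 50 | 71 |
| 28 (week 4) | 43 | 50 | 50 | 71 |
| 36 (week 6) | 51 | 58 | 54 | 75 |
| 42 (week 6) | 57 | 64 | 60 | 81 |

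**Early start, failure route.** A day-15 starter is on 20 mcg/h from day 30 and off by day 37, before the week-7 window opens on day 40. There is no on-drug EKG. The same holds for any start with s + 22 ≤ 40, that is, up to day 18.

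**Week-6 start.** In nominal week 7 the dose is 10–15 mcg/h for starts on days 36–37 and 5–10 mcg/h for days 38–42. With the window, an EKG at 20 mcg/h needs s + 15 ≤ 52, so s ≤ 37. Only two of the seven start days qualify. At week 12 the failure route has been off the patch since day 58–64. On the taper route the patient is off from day 75–81, so in nominal week 12 is off or on 5 mcg/h. Either way there is no EKG at 20 mcg/h.

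**Week-4 start.** A day-28 starter is on 20 mcg/h throughout days 43–49. A day-22 starter who fails is on it until day 44. Week 7 therefore largely covers this group.

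**Hold.** If QTc above 500 ms is found at week 7, the next named EKG is at week 12, 78 − 43 = 35 days later, and then only for a patient on the patch.

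**Denominator.** The number never measured, k, is unknown; take k = 0, 2 or 5 of 20 treated as an assumption. With no events, the one-sided 95% upper limit is 1 − 0.05^(1/(20 − k)): 13.9%, 15.3% or 18.1%.

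**The case against.** The strongest reply has four parts.

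1. **These are particular paths.** Most patients are expected to start by week 4, where coverage is good, and Section 5.1 expects moderate to severe pain to last to week 12 in most patients. A week-6 starter who stays on 20 mcg/h until then is measured at that dose. This stands: the gap can occur; it does not always occur.
2. **The window helps.** A reader might infer that a week-6 starter is never above 15 mcg/h at the week-7 EKG. The 3-day window rules that out for starts on days 36 and 37.
3. **The taper can be read more slowly.** If the first cut comes a week after control, each step moves 7 days later. A day-36 starter is then on 5 mcg/h from day 75 and off on day 82; a day-42 starter is on 10 from day 74 and 5 from day 81. Some patients then have a week-12 EKG, but still not at 20 mcg/h.
4. **The hold rule implies an EKG.** A reader might infer that the hold rule cannot work. That goes too far: Section 6.2.1 follows adverse events until resolution, and a threshold of 470 ms cannot be applied without a measurement. Section 4.1 also leaves room to regard a held patient as still on treatment. What remains is that no repeat EKG is named or timed. On the generous reading the next one is at week 12, when the regimen is due to end.

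**Conclusion.** The point holds as a gap that some patients can fall into. Starts up to day 18 that fail every step at the fastest pace can leave the patch with no on-drug EKG. Starts on days 38–42 cannot be measured at 20 mcg/h in week 7, and are not measured there in week 12 if they taper or fail as worked above. Read literally, a held patient has no scheduled EKG. The result assumes titration at the minimum interval and the titration and taper rules as written; slower escalation would put some early starters on the patch in week 7.

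Two further readings are not supported. A reader might infer that the QTc entry limit conflicts with later dosing. It is worded "Prolonged QTc greater than 450 milliseconds in males and greater than 470 milliseconds in females at the time of enrollment", and nothing in the protocol requires a recheck before the first dose. A reader might also take the calendar grid, where the first on-study EKG appears under week 6, as a second schedule. The oral-image row looks displaced against its own footnote in the same way, so this may be a table artefact, and nothing here relies on it.

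This is worth correcting before the safety table is fixed, but it is not a threat to the trial's main result.

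**What to change.** - **Protocol.** Reconcile footnote 7 and Sections 4.8 and 4.9 with exclusion 15 in Section 4.10, Section 5.4, Section 7.1.5 and Table 4, so that the EKG schedule and its on-patch condition are consistent with a variable drug start and with the hold and restart rule. Check the calendar mark against the source table. The sponsor's clinicians decide the timing; this review proposes none.
- **Section 8.6.** Report QTc above 500 ms over treated patients with at least one on-drug EKG. Give the dose at that EKG and the number of treated patients never measured, instead of a percentage of all treated patients alone.
- **Cost.** Wording edits, one extra line in the safety table and a smaller QTc denominator. Whether the number of EKGs changes depends on how the clinicians resolve the schedule.
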